3.3 Study Definitions and Derived Variables

The following definitions and derivations will be used in this study:

 Diarrhea is defined as ≥ 3 unformed or loose stools (mixed liquid and solid components) in a 24 hour period or at least 1 bloody loose or liquid stool or 1-2 liquid stools with at least some dehydration.

- 2. If a participant meets the definition of diarrhea, the start of the diarrhea episode will be the time of the first unformed stool which contributes to meeting the definition and the end of the diarrhea episode will be the time of the last unformed stool. If there is greater than 24 hours between loose or unformed stools then the illness will stop and a new AE will begin.
- 3. Mild diarrhea is defined as at least 3 looser than normal stools without dehydration in a 24 hour period.
- 4. Moderate diarrhea is defined as at least 3 looser than normal stools with dehydration in a 24 hour period.
- 5. Severe diarrhea is defined as at least 3 looser than normal stools with severe dehydration.
- 6. The baseline value will be defined as the last value obtained prior to the first vaccination of study product.
- 7. The reference day will be the day of the first vaccination and will be referred to as Day 1.
- 8. Study days prior to vaccination will be dependent upon the first dose of the vaccine. If the assessment occurred prior to the first dose, study days will be calculated by taking the date minus the first vaccination date (reference day).
- 9. Study days occurring on or after the date of vaccination will be dependent upon when the assessment occurred. If the assessment occurred on or after the first vaccination but prior to the second vaccination, study days will be calculated by taking the date minus the first vaccination date (reference day) and adding 1. If the assessment occurred on or after the second vaccination, then study days will be calculated by taking the date minus the second vaccination date and adding 1.
- 10. Age will be calculated from the date of enrollment and will be presented in whole years for adults and in months for children under 5 years of age (truncated integer).
- 11. The calculations for GMTs will be performed by taking the anti-log of the arithmetic mean of the log₁₀-transformed titers.
- 12. Fold increase/rise will be calculated as the following:
 - a. For fold rise compared to baseline: ratio of: $\frac{post-immunization\ titer}{pre-immunization\ titer}$

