4.3.1 Inclusion Criteria

4.3.1.1 Inclusion Criteria: Part A - Adult

Male and female participants will be eligible for inclusion if ALL of the following apply at the time of screening:

- 1. Healthy male or female adults 18-45 years old, inclusive.
- 2. General good health as determined by the screening evaluation no greater than 7 days before enrollment and vaccination.
- 3. Properly informed about the study, able to understand it and sign or thumb print consent form.
- 4. Available for the entire period of the study and reachable by study staff throughout the entire follow-up period.
- 5. Female of childbearing potential willing to take a urine pregnancy test at screening and before the second vaccination. Pregnancy tests must be negative before each vaccination. Females of childbearing potential must agree to use an efficacious hormonal or barrier method of birth control during the study. Abstinence is also acceptable.
- 6. Informed Consent (signature or thumb print provided, with witness signature).

4.3.1.2 Inclusion Criteria: Parts B, C and D – Toddlers, Younger Children, and Infants

Male and female participants will be eligible for inclusion if ALL of the following apply at the time of screening:

- 1. Healthy male or female toddlers/younger children/infants ages:
 - a) Part B: \geq 24 and \leq 59 months old toddlers at the time of enrollment.
 - b) Part C: ≥12 and <24 months old younger children at the time of enrollment.
 - c) Part D: \geq 6 and \leq 12 months old infants at the time of enrollment.
- 2. General good health as determined by the screening evaluation no greater than 7 days before enrollment and vaccination.
- 3. Parent properly informed about the study, able to understand it and sign or thumb print the informed consent form.
- 4. Parent and child available for the entire study period of the study and reachable by study staff throughout the entire follow-up period.
- 5. Informed Consent (signature or thumb of parent, with signature of witness, provided)

4.3.1.3 Continued Inclusion Criteria:

Fulfilment of all of the following continuing eligibility criteria is required for all participants to receive their second vaccination (Day 14).

- 1. Participant available for study evaluations and reachable by study staff throughout the entire follow-up period.
- 2. Continued informed consent.

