4.5.1 Safety Variables

The safety variables to be assessed are adverse events (AEs), serious adverse events (SAEs), and multiple clinical safety laboratory measurements [including white blood cells (WBC), hemoglobin (Hgb), platelets, differentials (neutrophils and lymphocytes), alanine aminotransferase (ALT), albumin, total bilirubin and serum creatinine], physical exam, and vital sign parameters. Solicited systemic reactogenicity events within 7 days of each vaccination will be collected. If a solicited sign or symptom has started during the seven days post-vaccination and continues, it will continue to be reported as a reactogenicity symptom. Only when the reactogenicity event is considered an SAE, as defined below, will it be reported on an AE/SAE form in addition to the reactogenicity form. Any symptom starting after seven days post-vaccination will be recorded as an AE. Unsolicited AEs will be collected through the Day 42 visit. SAEs will be collected through six months after the first vaccination or the duration of the study.

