6.3.2 Safety Population

All participants in the enrolled population who receive a study vaccination and have safety data available will be included in the safety population. Treatment groups for safety analysis will be assigned according to the actual treatment received at the first vaccination. If a participant receives mixed doses (e.g., an ETVAX dose without dmLT at Dose 1 and the same ETVAX at Dose 2 with dmLT), the safety data collected after the start of the mixed dosing (e.g., post Dose 2) will be excluded from the analysis. All excluded data will be presented in the data listings. All safety analyses will be performed using this population.

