6.5 Missing Data

In general, all missing data will be treated as missing completely at random and no imputation will be performed except for the safety endpoints as described below. Non-analyzable data (e.g., due to major protocol violations) will be documented in the deviations.

If some safety data are available for a participant in the FA population, but respective secondary endpoint related data are missing, then the participant will be included in the safety analysis and data will be treated as follows for immediate AEs, unsolicited AEs and serious adverse events (SAEs).

- 1. If Severity is missing for any AE, then it will be considered as an AE of maximum severity (Grade 3) "Severe", unless it is captured as SAE.
- 2. If "Relationship" is missing, then it will be considered as "Related" to the vaccine administered.
- 3. If, for Start date, the day of event/condition is missing due to any adverse event, then it will be imputed as the date of last dose of study vaccine.
- 4. If the Stop date of an adverse event is missing, then it will be treated as ongoing.

For solicited adverse events, the following assumptions will be made:

- 1. If dates are missing, but symptoms are reported, then the day post vaccination will be used to calculate the date of the symptom.
- 2. If a symptom is not reported at any time through Day 7, then no imputation for missing data will be performed. The data will be summarized as not reported on the tables.

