9.1.2 Unsolicited Adverse Events

The proportion of participants reporting at least one unsolicited adverse event will be summarized by MedDRA system organ class and preferred term for each treatment group and overall. Denominators for percentages are the number of participants in the Safety population. A 95% CI calculated using Clopper-Pearson methodology from a binomial distribution (SAS Proc Freq with a binomial option) will be presented for each MedDRA system organ class and preferred term (Tables 14.3.1.7(a)(b)(c)(d))

Unsolicited adverse events by participant will be presented in Listings 16.2.7.2(a)(b)(c)(d).

The following summaries for unsolicited adverse events will be presented by treatment group:

- Participant level summary of maximum severity and relationship to study product by MedDRA SOC and PT (Tables 14.3.1.8.1(a)(b)(c)(d));
- Participant level summary of related unsolicited events by maximum severity, MedDRA SOC and PT (Tables 14.3.1.8.2(a)(b)(c)(d));
- Participant incidence of unsolicited adverse events over time by MedDRA SOC and PT (Days 1-8, Days > 8) (Tables 14.3.1.9.1(a)(b)(c)(d));
- Participant incidence of related unsolicited adverse events over time by MedDRA SOC and PT (Days 1-8, Days > 8) (Tables 14.3.1.9.2(a)(b)(c)(d));
- Total frequency of adverse events over time by MedDRA SOC and PT (Days 1-8, Days > 8) (Tables 14.3.1.10(a)(b)(c)(d));
- Participant listing of non-serious adverse events of moderate or greater severity (Tables 14.3.2.2(a)(b)(c)(d));
- Bar chart of the frequency of events for non-serious adverse events by maximum severity and MedDRA SOC (Figures 14.3.1.11(a)(b)(c)(d));
- Bar chart of the percent of participants reporting a non-serious adverse event by maximum severity and MedDRA SOC (Figures 14.3.1.12(a)(b)(c)(d));
- Bar chart of the frequency of any adverse event by maximum severity (Figures 14.3.1.13(a)(b)(c)(d));
- Bar chart of the percent of participants of any adverse event by maximum severity (Figures 14.3.1.14(a)(b)(c)(d));
- Bar chart of the frequency of non-serious adverse events by relationship to treatment and MedDRA SOC (Figures 14.3.1.15(a)(b)(c)(d));

- Bar chart of the percent of participants of non-serious adverse events by relationship to treatment and MedDRA SOC (Figures 14.3.1.16(a)(b)(c)(d));
- Bar chart of the frequency of any adverse event by relationship to treatment (Figures 14.3.1.17(a)(b)(c)(d)).

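### The missing-start-day rule puts an adverse event on a dose date even when its recorded month or stop date rules that date out

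*SAP*

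**What the plan says.** The third rule in SAP Section 6.5 deals with incomplete start dates. Where no day has been recorded, the instruction reads "then it will be imputed as the date of last dose of study vaccine". The section introduces its four rules with the words "data will be treated as follows for immediate AEs, unsolicited AEs and serious adverse events (SAEs"), so solicited events are outside them and have their own date rule. The trigger is the missing day alone. Nothing in the section asks whether the month and year are known, whether the stop date comes earlier, or which dose preceded the event. No other section limits the rule.

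Three other places decide what the imputed date does:

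- Section 3.3, item 9, restarts the day count at dose 2: "study days will be calculated by taking the date minus the second vaccination date and adding 1".
- Section 9.1.2 plans tables of unsolicited events split at Day 8 (Tables 14.3.1.9 and 14.3.1.10). The shells label the same split Days 0-7 and Days 8+.
- Section 6.3.2 provides that, in a participant given mixed doses, "the safety data collected after the start of the mixed dosing (e.g., post Dose 2) will be excluded from the analysis".

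**The concern.** A partial date with month and year recorded is the usual kind, and it carries information. The rule discards it. An event recorded in the month after dose 2 is written down as starting on the day of dose 2, although the record shows that it did not.

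At stake are the time-since-dose tables, the days-post-dose and duration columns of Tables 14.3.2.1 and 14.3.2.2, and Listing 16.2.7.2. Safety is the primary objective and most arms have 15 participants, so a few misplaced events can change how a window looks.

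The phrase 'last dose' is also open. It may mean the final dose received or the most recent dose before the event. Some consequences depend on which is meant, so they are kept apart below.

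**Working it through.** **Inputs.** Section 4.3.1.3 places dose 2 at Day 14 ("required for all participants to receive their second vaccination (Day 14")). Section 4.5.1 states: "Unsolicited AEs will be collected through the Day 42 visit". Section 4.5.1.3 collects SAEs for 182 days. Section 5 gives arms of 15, or 30 in infants. For the count below, doses are set at Day 0 and Day 14 and onset days run from 0 to 42, which is 43 days. Equal weight on each day is an assumption made only for illustration. The plan states no figure to reproduce.

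**Where an imputed event lands.** Dose date minus dose date plus 1 = Day 1, or Day 0 in the shells. Either is in the early window, so every imputed event goes there.

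**Onset days that belong in the late window.** More than 7 days after the preceding dose means Days 8-13 (6 days) and Days 22-42 (21 days). 6 + 21 = 27, and 27/43 = 63%. This holds under either reading of 'last dose'.

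**Contradiction of the month.** Over 366 possible dose-1 dates, 366 × 43 = 15,738 combinations of dose date and onset day were counted. The true onset lies in a different month from the imputed date in 39% of them if 'last dose' is the final dose, and in 38% if it is the most recent dose. These overlap with the 63% and must not be added to it.

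**Example, either reading.** Doses on 10 and 24 March; event on Day 35, that is 14 April, recorded as April with the day missing. The rule gives 24 March, which is 35 − 14 = 21 days early. The recorded month alone settles the window: the earliest possible start, 1 April, is 8 days after dose 2, so Day 9 by Section 3.3. That is late under both labels.

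**Example, final-dose reading only.** Doses on 25 March and 8 April; event recorded as March, stopped on 30 March. The rule gives a start of 8 April, 9 days after the stop, and credits the event to dose 2. Of the 43 onset days, Days 0-13 precede dose 2: 14/43 = 33% would move from dose 1 to dose 2. Under the most-recent-dose reading this shift disappears.

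**Size per participant.** One participant moved between windows changes a window-specific proportion by up to 1/15 = 6.7 percentage points, or 1/30 = 3.3 in an infant arm. This is the weight of one event, not an estimate of total impact. An SAE late in the 182 days can be moved by months.

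**The case against.** The strongest defence is that the rule is deliberately worst-case. The two rules before it set missing severity to severe and missing relationship to related, and placing an event at vaccination follows the same logic: it overstates a temporal link and hides nothing. That is fair when the date is truly unknown. It does not justify contradicting a recorded month or stop date.

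The second defence is that 'last dose' means the most recent dose, in line with the way Section 3.3 counts days. If so, the shift between doses and the starts after stops both go. The SAP does not say this, and the window error remains on that reading.

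Third, a reader might infer that the primary AE proportions are distorted or that events are routinely lost. The documents do not support that. Table 14.3.1.7 counts each participant once over the Safety population with no time window, so moving a start date leaves it unchanged. Section 9.1.2 plans no between-group test of unsolicited events. Loss from the analysis needs four things together: the final-dose reading, a mixed-dose participant, an event after dose 1 with the day missing, and Section 6.3.2 applied by imputed onset. That section speaks of when data were collected, and it keeps excluded data in the listings.

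Finally, close follow-up may make partial dates uncommon. That stands, because the SAP gives no number.

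**Conclusion.** The rule as written gives wrong results whenever the recorded month or the stop date excludes the dose date. Under either reading, late events enter the early window of descriptive Tables 14.3.1.9 and 14.3.1.10, and days post dose and duration are wrong in the listings. Attribution of dose-1 events to dose 2 and starts after stops follow only if 'last dose' is the final dose. Exclusion under Section 6.3.2 is possible only in the narrow case above. Overall AE and SAE proportions are otherwise unaffected.

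The 63%, 39%, 38% and 33% are shares of possible onset days under a 14-day interval and equal weighting. They are not expected error rates. Part of the window error cannot be avoided: for an event 21 days after dose 2, the month differs from that of dose 2 on 12 × 21 = 252 of 365 dates (69%). On the other 31% a missing day leaves nothing to correct it with. The change is worth making because it is cheap and the table errors are avoidable, not because a primary endpoint is at risk.

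**What to change.** In Section 6.5:

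1. Define 'last dose' as the most recent dose compatible with the known month and year and not after the stop date, or the report date if known.
2. Impute that dose date only if it falls in the known month; otherwise use the first day of the known month.
3. Keep the present rule only when month and year are missing too, and subject to the stop date.
4. State that an imputed date alone cannot trigger the Section 6.3.2 exclusion.

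In the examples, the April event becomes 1 April (Day 9, late window) and the March event becomes 25 March, credited to dose 1 and before its stop.

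The cost is a short edit and a few lines of code, with no change to data collection. One limit remains. Both doses fall in the same month for (365 − 12 × 14)/365 = 54% of dose-1 dates. Where neither the stop date nor the report date separates the doses, choosing the later one is a convention and should be labelled as such.

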6.6 Interim Analyses and Data Monitoring

Extensive safety monitoring will be provided for this protocol. The PI and/or designated site staff will be responsible for continuous close safety monitoring of all study participants and for alerting the Sponsor if unexpected concerns arise or stopping criteria are met.

6.6.1 Safety Oversight

A Data and Safety Monitoring Board (DSMB) will be formed by the Ethical Review Committee (ERC) to evaluate and assess the safety of study participants. In addition, an Independent Protocol Safety Team (IPST) will be formed for the study and will carry out the safety and clinical evaluation of the icddr,b. Moreover there will be a team comprised of the study physician, the Emmes medical monitor, the PI, and the Medical Officer from PATH for evaluation of the study at different intervals during the study.

Before enrolling participants in subsequent cohorts within an age group, the safety data from the previous cohort(s) will be evaluated and reviewed by the IPST. These data include, but are not limited to, physical examinations, vital signs, and solicited reactogenicity symptoms. The IPST will convene after each cohort

within an age group to review data through Day 4 after the second vaccine administration and make a recommendation to the Sponsor on whether to proceed to the initiation of the following cohort.

The DSMB will be composed of 3-4 members, two of which are nominated by the ERC chairperson. The PI also has the option of nominating 1-2 members with therapeutic expertise. The DSMB meets before study initiation, prior to age de-escalation, and after the study closeout. The PI can also request a DSMB meeting depending upon the study complexity or in light of study concerns. The DSMB will advise the PI of its findings and provide recommendations. The DSMB will review all unanticipated problems involving risk to the participants or others, serious adverse events, and all participant deaths associated with the protocol. The PI will inform the Emmes Medical Monitor and the PATH Medical Officer in detail about the discussions of those meetings.

6.6.2 Study Pause

Study pause is defined as a decision to cease, temporarily or definitely, enrollment and all vaccinations. Study pause or final cessation of vaccinations will not eliminate any safety follow-up procedures specified by the protocol. The Sponsor will pause vaccinations in the study if the IPST, DSMB or protocol team including the PATH Medical Officer and Emmes Medical Monitor, determines that study hold criteria have been met, or in the event of any other safety concerns.

The following study pause rules will automatically pause or halt further vaccinations until the protocol team consisting of the PI, study physician, independent medical monitor, PATH Medical Officer and Emmes Medical Monitor, has performed a review. However participants already enrolled will continue to be followed for safety during the pause. These pause rules refer to suspected adverse reactions and will be triggered automatically if any of the events described below are met during the conduct of the study:

- One participant death from Day 0 to Day 42, unless judged definitely unrelated to vaccination;
- One participant with a serious AE (SAE) judged as definitely or probably related to vaccine;
- >2 participants in a cohort with the same ≥ grade 3 (severe) solicited AE within three days following vaccination judged as definitely or probably related to vaccine;
- >2 participants in a cohort with the same \geq grade 3 (severe) abnormal clinical monitoring laboratory value (7 days following vaccination) judged as definitely or probably related to vaccine;
- >2 participants in a cohort with the same ≥ grade 3 (severe) AE judged as definitely or probably related to vaccine.

6.6.3 Interim Analysis and Future Planning

Early final analysis of each Part when all cohorts within the Part have completed the primary safety and immunogenicity follow-up (Day 43, 28 days post last vaccination) may be performed to facilitate the decisions external to the study conduct. The unblinded analysis will be performed by an independent statistician who is not involved in the conduct of the study after all data have been cleaned and locked through Day 43 follow-up for all participants in each Part. Analysis will be presented in group unblinded fashion and no individual listing will be generated. These analyses would not otherwise alter the course of the trial and blinded status of the study for investigators and study participants until the completion of the study.

6.7 Multicenter Studies

This is a single site study.

6.8 Multiple Comparisons/Multiplicity

This is an exploratory study in descending age groups. Due to the exploratory nature of all of the statistical comparisons for immunogenicity endpoints, there will not be an adjustment for multiple comparisons across the entire study. However, within each immunogenicity endpoint for each age group, the Holm-Bonferroni correction for multiple testing will be applied to control the multiple comparisons associated with multiple treatment groups. It is acknowledged that there will be inflated Type I errors (i.e., inflated false statistical significances) from performing multiple unadjusted comparisons.

7 SUMMARY OF STUDY PARTICIPANTS

7.1 Participant Disposition

Screened participants who were ineligible for enrollment in the study will be presented by inclusion and exclusion criteria and other reasons for ineligibility (Table 14.1.1(a)(b)(c)(d)). The composition of analysis populations, including reasons for participant exclusion, by treatment group, is presented in Table 14.1.2(a)(b)(c)(d).

The disposition of participants in the study will be tabulated by treatment group and overall (Table 14.1.3(a)(b)(c)(d)). This table will show the number of participants screened, enrolled, received first vaccination, received second vaccination, completed Visit 7 (Day 43), completed follow-up, in FA Population and in PP population.

A flowchart presenting the disposition of study participants, adapted from the CONSORT statement [32] will be included (Figure 14.1.1(a)(b)(c)(d)). The flowchart includes the number of participants eligible, enrolled and randomized, lost to follow-up, and analyzed, by treatment group.

A listing of participants who discontinued or terminated early from the study and who were excluded from the Safety population, the FA population and the PP population will be included in Listings 16.2.1(a)(b)(c)(d) and 16.2.3(a)(b)(c)(d), respectively.

